***2.4.5.3 Analyses of vital signs variables***

Summary statistics of all laboratory variables (number, mean, standard deviation, median, first quartile, third quartile, minimum, and maximum) will be calculated for each visit or study assessment by treatment group during the treatment period.

## 2.5 Data handling conventions

### 2.5.1 General conventions

The date of the last dose of IMP is equal to the last date of administration reported on the IMP administration case report form page.

The following formulas will be used for computation of parameters.

#### *Renal function formulas*

The estimated GFR (mL/min/1.73 m^2) will be calculated using the 4 variable Modification of Diet in Renal Disease (MDRD) formula:

Standard unit:  $eGFR \text{ (mL/min/1.73 m}^2\text{)} = 175 \times [\text{Serum Creatinine } (\mu\text{mol/L})/88.4]^{-1.154} \times \text{Age (year)}^{-0.203} \times 1.212 \text{ (if Black)} \times 0.742 \text{ (if female)}$

### 2.5.2 Data handling conventions for secondary efficacy variables

Rules defined for the primary efficacy variable will apply to time-to-event of secondary efficacy variables.

### 2.5.3 Missing data

For categorical variables, patients with missing data are not included in calculations of percentages unless otherwise specified. When relevant, the number of patients with missing data is presented.

Derived variables will be considered missing if any of the original variables required to calculate them are missing. For example, if either a baseline assessment or an endpoint assessment is missing for a particular patient, then change from baseline at endpoint will be missing. Depending upon the assessment, analyses may not include all patients in the analysis population, because certain patients in the intended population may have missing data.

#### *Handling of missing or incomplete dates of time-to-event efficacy endpoints*

Rules for imputations are detailed in Appendix A Assignment of dates to events.

#### *Handling of computation of treatment duration if IMP start of treatment date is missing*

Date/time of first administration is the first non-missing start date/time of double-blind IMP completed in the e-CRF 'First dose IMP' form.

For a patient who was randomized and dispensed a double-blind treatment kit:

- If the date of first IMP is missing, the date of the first IMP administration will be set to the date of randomization.
- If the date of first administration is partially missing with the month and year present, the day will be set to the date of randomization if randomization was in the same month. If

randomization was in the month prior to the first drug administration the missing day will be imputed as the first day of the month.

A patient who is randomized but not exposed is identified by ‘Not taken’ ticked in the e-CRF ‘First does IMP’ form.

***Handling of adverse events with missing or partial date/time of onset***

Missing or partial adverse event onset dates and times will be imputed so that if the partial adverse event onset date/time information does not indicate that the adverse event started prior to treatment, the adverse event will be classified as occurring after treatment initiation. No imputation of adverse event end dates/times will be performed. These data imputations are for categorization purpose only. There is no imputation for date/time of adverse event resolution.

***Handling of adverse events when date and time of first IMP administration is missing***

When the date and time of the first IMP administration is missing, adverse events will be considered to occur after treatment initiation if they occurred on or after the day of randomization.

***Baseline definition for efficacy data***

The baseline for a given parameter is defined as the last available measurement, including unscheduled assessments, assessed prior to the first administration of double-blind IMP or the last available value before randomization if not treated with double-blind IMP.

**2.5.4 Windows for time points**

Data analyzed by time point (laboratory safety data, vital signs, KCCQ-12) will be summarized using the time windows given the table below. These time windows will be applicable for all analyses, and they are defined to provide more homogeneous data for time point-specific analyses that the visit windows specified in the protocol. If multiple values of a parameter are available in a time window, the last will be used in a given analysis.

**Time windows definitions**

Time point	Targeted study day	Time window
Date of Randomization	1	n/a
Week 1	8	5 to 11
Week 2	15	12 to 18
Week 4	29	22 to 36
Week 16 (Month 4)	113	85 to 141
Beyond Week 16	Number of weeks of the planned visit x 7	Targeted study day $\pm$ 28 days

## **Appendix A Assignment of dates to events**

This section describe the calculation of the time to event and the time that patients without event and were in the study (under risk).

For patients with an event, the time to event is calculated as:

$$\text{Date of event} - \text{start date} + 1$$

For patients without an event, the time at risk is calculated as:

$$\text{Date of censoring} - \text{start date} + 1$$

For specific analysis, events that occur any time during the data period of the corresponding analysis will be considered as eligible events.

### ***Start date***

In general, the start date of an efficacy event will be the date of randomization unless otherwise specified. However, the date of first IMP taken will be used as the start date for the analysis (analyzed as occurrence of and time to first event) of following events:

- AE (including AE, AESI, EOSI)

### ***Onset of event (date of event)***

For composite outcomes, e.g. time to CV death and HHF, the earliest onset date of the corresponding components will be used.

For events, which are included as a fatal and non-fatal component into a composite endpoint (applies only to MI and stroke), the onset of the event is considered for the derivation of time to first occurrence, not the date of death.

For all other CV death types (e.g. sudden death) the date of death is used.

The time to death will be used for CV death and all-cause mortality rather than the time to onset of the associated event causing the death. For example, if a patient has a fatal stroke that leads to death several days later, the date of death (a later date) will be used rather than the date of stroke onset.

### ***Censoring***

The underlying rule for censoring is that the censoring date should be the last date the patient is known to be free of the event endpoint (free of each component for composite endpoint).

#### ***a. General censoring rule for primary efficacy endpoint:***

For patients who have no primary CV endpoints, they will be censored using the following rules:

- Patients who completed the study will be censored at their last study visit date (study close-out visit date or final follow-up visit date, whichever later).  
Note: If there are CV events happening after the patient's last study visit and the event's proceeding/related event's onset date is on or before the patient's last study visit date, in this case, this CV events will be included in efficacy analysis.

Another example, for a HHF, if the onset date of HF is before last study visit and its resulted hospitalization is after last study visit, this HHF will be included in efficacy analysis.

- Patients who died without discontinuing the study before death (ie Death reported on the 'Completion of End of Study') will be censored at their date of Non-CV death
- Patients who discontinued the study will be censored at their later of study discontinuation date or latest date with cardiovascular efficacy endpoint information (MI/UA, heart failure, cerebrovascular event, or coronary procedure, admission to hospital/emergency room, cardiac biomarkers) collected

**b. Specific censoring rule for all-cause mortality**

Patients who did not die will be censored at the latest date of: end of study visit date, date of vital status (if alive), or date last known to be alive (if LTFU). Usually, this is the date of 'Date of last available information' in 'Subject Status' form for patient alive at that date.

**c. Specific censoring rule for eGFR endpoint only**

Patients without an event will be considered censored at their earlier of last laboratory sample date where eGFR results are available.

Patients who already fulfil the respective condition at baseline or without post-baseline laboratory measurements will be censored at Day 1.

**d. Specific censoring rule for composite renal endpoints**

Patients without the event will be considered censored at their earlier of last laboratory sample date where eGFR results are available. If a patient doesn't have the eGFR measurements after a certain timepoint, but a dialysis procedure not meeting the definition of chronic occurs after the last eGFR measurement but before the patient's last study visit date, the patient will be censored at the last start date of dialysis.

Patients who already fulfil the respective condition at baseline or without post-baseline laboratory measurements will be censored at Day 1.

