**2.1.3 Efficacy endpoints**

Efficacy endpoint events with onset date prior to randomization will not be included in efficacy analysis and instead will be treated as pre-treatment adverse events.

In the analyses of time-to-event efficacy endpoints:

- Deaths not included among the events in the endpoint will be treated as competing events;
- Patients alive at the end of the study will be right censored on the date they were last known to be alive;
- Event types and dates included in the analyses will be those as reported by the investigators; and
- In the case where the exact date of occurrence of an event is not known (the day, month, and/or year are missing), the date will be imputed as described in Appendix .

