##### 2.4.4.1 Analyses of primary efficacy endpoint

The analysis of the primary efficacy endpoint will be the comparison between the two treatments using a Wald test stratified by region (North America, Latin America, Western Europe, Eastern Europe, and rest of world) and LVEF (<50%, ≥50%). This primary comparison will be a 2-sided test at the 0.05 type 1 error level for the following hypothesis:

H0: HR=1 versus H1: HR ≠1

The estimates of the hazard ratio (HR) and corresponding 2-sided 95% confidence interval (CI) will be provided by a marginal Cox proportional hazard model stratified by region and ejection fraction, with non-cardiovascular (non-CV) death treated as a competing event. By using a robust sandwich covariance matrix estimate, the model allows for the possibility of multiple events within a given patient. If a given patient has more than one event on a given day, the event times will be varied by 0.1 day so that every event time is unique.

To determine whether the treatment effect on the primary endpoint is different before and after 240 days (the end of the window for up-titration of dose), a marginal proportional hazards model that allows the treatment HR to vary before and after 240 days will be compared with the model in which the treatment HR is assumed constant over time, to test whether a nonconstant HR provides a better fit to the observed data.

As a sensitivity analysis, an on-treatment analysis will be performed for the primary endpoint, using the same method above but only including events through 30 days after last dose. Another on-treatment sensitivity analysis will include only events through 7 days after last dose.

The cumulative incidence function (CIF) will also be constructed to estimate the primary efficacy endpoint rate by treatment group. The absolute risk reduction (ARR) will be estimated by the difference between treatment groups in the number of events per 100 patient-years of follow-up. Results will be provided for both the primary efficacy endpoint overall and its individual components (CV death, HHF, urgent HF visit). In addition, a figure summarizing the numbers of first and subsequent events will be constructed for the primary endpoint. Bars for sotagliflozin and placebo will be provided for the numbers of first events, second events, and a category of “third and subsequent events.” Within each bar the number of CV death, HHF, and urgent HF visit events will be separated by color.

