#### ***2.4.4.4 Additional efficacy analysis(es)***

Time-to-event other efficacy endpoints will be analyzed using the same statistical methodology as for the primary endpoint. If the endpoint concerns the first event, then only the first event experienced by a given patient will be included in the analysis. Deaths that are not part of a given endpoint will be treated as competing events.

For the analyses of DAOH and PDAOH, total potential follow-up time for each patient is defined as the number of days from date of randomization until the patient's date last known alive, or May 1, 2020 (the date sites were instructed to complete end of study contacts with patients; patients known to have died after this date will be censored as alive as of May 1, 2020) if the patient died. The total number of days spent in hospital will be derived from the investigator reports. If a patient died, the number of days dead will be calculated as the time interval between their date of death and May 1, 2020. DAOH will be calculated by subtracting days in hospital and days dead from total potential follow-up time; if a patient survived without hospitalization, DAOH will be equal to the potential follow-up time for that patient.

DAOH, days dead, and days in hospital will be compared between treatment groups by rate ratios (RRs) from a Poisson regression model with a log link function and Pearson  $\chi^2$  scaling of standard errors to account for potential overdispersion. In addition to treatment group, the logarithm of potential follow-up time will be used as an offset variable in the model. Given the expectation that a fraction of patients will survive without hospitalization until the end of follow-up (i.e., PDAOH =100%), PDAOH will be compared between treatment groups with one-inflated beta regression. In this application, the model will jointly estimate the treatment odds ratio (OR) of surviving until the end of the study without hospitalization (ie, PDAOH =100%), and the treatment OR of higher mean PDAOH among the subset of patients who died or had at least one hospitalization or died during follow-up (i.e., PDAOH <100%). Plots of the distribution of DAOH will be constructed,

as well as summaries of reasons for hospitalizations (e.g., HF, other efficacy event, non-efficacy adverse event, etc.).

Changes from baseline in NT-proBNP, hematocrit, HbA1c, body weight, and SBP will be analyzed using the same methods as for change in eGFR.

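### SAP Appendix A d gives no date or status for patients who die without a renal event, which conflicts with the SAP's own rule that such deaths are competing events

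*SAP*

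**What the plan says.** The renal composite is listed in SAP 2.1.3.3 among the other efficacy endpoints. Its components are a sustained eGFR fall of at least 50%, a sustained eGFR below 15, chronic dialysis and renal transplant. Death is not a component.

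The main text gives these rules for such an endpoint:

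- SAP 2.1.3, for all time-to-event efficacy endpoints: "Deaths not included among the events in the endpoint will be treated as competing events". The next item limits right censoring to survivors: "Patients alive at the end of the study will be right censored on the date they were last known to be alive".
- SAP 2.4.4.4, for the other endpoints: "Time-to-event other efficacy endpoints will be analyzed using the same statistical methodology as for the primary endpoint", and again: "Deaths that are not part of a given endpoint will be treated as competing events".
- SAP 2.4.4.1, the source of that methodology: "The cumulative incidence function (CIF) will also be constructed to estimate the primary efficacy endpoint rate by treatment group".

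Appendix A d is headed as a specific rule for composite renal endpoints. Its base rule is: "Patients without the event will be considered censored at their earlier of last laboratory sample date where eGFR results are available". There are two exceptions. If a non-chronic dialysis follows the last eGFR, "the patient will be censored at the last start date of dialysis". And: "Patients who already fulfil the respective condition at baseline or without post-baseline laboratory measurements will be censored at Day 1".

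**The concern.** A patient who dies without a renal event has two incompatible codings. Under the main text the patient is a competing event at the date of death. Under Appendix A d the patient falls among those without the event and is an ordinary censored observation on an earlier date.

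The choice matters most for absolute risk. If deaths are coded as censoring, the cumulative incidence estimator treats people who have died as if they could still reach a renal event. The result describes a population in which nobody dies. The excess is larger in the arm with more deaths, so an absolute difference between arms would also be distorted if treatment affects mortality. SAP 1.1 has the efficacy analyses run by an independent statistician and verified separately by the sponsor's team, so two programmers could follow different rules in good faith.

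**Working it through.** **1. The rules side by side**

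| Patient without a renal event | SAP 2.1.3 and 2.4.4.4 | Appendix A d |
|---|---|---|
| Dies, has a post-baseline sample | Competing event | Censored at last eGFR sample |
| Dies, non-chronic dialysis after last sample | Competing event | Censored at last dialysis start |
| Dies, no post-baseline sample | Competing event | Censored at Day 1 |
| Alive | Censored when last known alive | Censored at last eGFR sample, last dialysis start or Day 1 |

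Other Appendix A rules do deal with death. Rule a uses the date of non-CV death, rule b is limited to patients who did not die, and rule e takes the earlier of a treatment-based date and death. Rule d has no such clause. Its comparison of dates also names only one date.

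**2. Size in closed form**

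The documents state no rate, event count or power for the renal composite, so there is no figure of the plan's to reproduce. The rates below are assumptions. With constant hazards r (renal) and d (death) and time t in years:

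- deaths as competing events: CIF = r/(r+d) × (1 − exp(−(r+d)t))
- deaths as censoring: 1 − KM = 1 − exp(−rt)

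At t = 1:

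| r | d | CIF | 1 − KM | Excess (points) | Relative |
|---|---|---|---|---|---|
| 0.02 | 0.10 | 1.88% | 1.98% | 0.10 | 5.1% |
| 0.02 | 0.25 | 1.75% | 1.98% | 0.23 | 13.0% |
| 0.03 | 0.20 | 2.68% | 2.96% | 0.28 | 10.3% |
| 0.05 | 0.10 | 4.64% | 4.88% | 0.23 | 5.0% |
| 0.05 | 0.25 | 4.32% | 4.88% | 0.56 | 12.9% |

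At t = 1.5 with r = 0.03 and d = 0.20: CIF = 0.03/0.23 × (1 − exp(−0.345)) = 0.1304 × 0.2918 = 3.81%, and 1 − exp(−0.045) = 4.40%. Over the same rate ranges the relative excess at 18 months is 8 to 20%.

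As an outer anchor, Protocol 4.3 cites 5-year survival below 25% in heart failure generally. That implies d of at least −ln(0.25)/5 = 0.277 per year. With r = 0.03 the 12-month excess is then 14.4%, or 0.37 points.

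**3. Size on the visit schedule**

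The literal rule also ends follow-up before death. A simulation placed eGFR samples at Days 8, 15, 29 and 113, then every 4 months, with a closeout sample for survivors. Follow-up was assumed to be 1 to 21 months because of the early stop. For r = 0.03 and d = 0.20, 16.3% of patients died without a renal event. The literal rule left none of them as competing events. The 12-month estimates were:

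- competing event at death: 2.63%
- censored at death: 2.89%
- literal Appendix A d: 2.97% (+13.0% relative)

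Of the 0.34-point excess, 0.26 comes from censoring deaths at all and 0.08 from stopping at the last sample. The direction does not depend on the assumed rates, since both steps can only raise the estimate.

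**4. Hazard ratios**

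These are averages over six simulated data sets per row, so compare within a row.

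| True HR, renal / death | Cause-specific, follow-up to death | Literal Appendix A d | Subdistribution (Fine-Gray) |
|---|---|---|---|
| 0.7 / 1.0 | 0.691 | 0.691 | 0.691 |
| 0.7 / 0.8 | 0.718 | 0.714 | 0.746 |

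SAP 2.4.4.1 calls for a marginal Cox model with a competing event and names neither type.

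**The case against.** The strongest reply is that nothing ranks Appendix A above the body of the SAP. The only precedence statement, in SAP 1.1, puts the SAP over the protocol. On this reading 2.1.3 separates deaths from censored patients, and Appendix A d only dates those who are to be censored. Appendix A is also loose with the word: rule a speaks of censoring at non-CV death, which 2.4.4.1 makes a competing event. This stands, and it makes the consequence conditional. It does not remove the conflict. Rule a at least supplies the death date, whereas rule d covers everyone without the event and supplies none.

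A reader might infer that no death can enter the renal analysis and that its incidence is therefore overstated. The documents do not support that as a fact, because a programmer who follows 2.1.3 would code the deaths correctly. The cumulative incidence function is also named only for the primary endpoint. It reaches the renal composite solely through the phrase about using the same methodology.

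Other replies stand in part. The hazard ratio, which the SAP clearly does require for this endpoint, hardly moves if it is cause-specific. For early deaths the gap from last sample to death can be days, since samples are dense in the first month. Last-sample censoring also has a stated basis: the introduction to the censoring rules in Appendix A asks for the last date on which the patient is known to be free of every component.

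**Conclusion.** The SAP contains an unresolved contradiction about patients who die without a renal event. If Appendix A d is applied as written, any renal cumulative incidence is overstated. Under the assumed rates the excess at 12 months is about 5 to 13% relative, roughly 0.1 to 0.6 percentage points. The direction is certain under that reading. The size rests on constant hazards and on rates the documents do not give. A subdistribution hazard ratio would change if treatment affects mortality, while a cause-specific one would hardly change.

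The consequence is limited. The composite is an other endpoint, outside the sequential testing in SAP 2.4.4.3, so a reader should not infer that any confirmatory conclusion depends on it. The point is minor but worth correcting, because following a stated rule gives a result contrary to the SAP's own competing-event rule.

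**What to change.** In Appendix A d, replace the base rule with: *Patients who die without the event are competing events at the date of death, including those with no post-baseline sample; patients not known to have died are censored at the last eGFR sample date, or at the last dialysis start if later.* Delete *earlier of*. The Day 1 rule can stay for survivors with no post-baseline sample and for patients who already meet the condition at baseline.

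Align rule c (eGFR endpoint only) for consistency. SAP 2.1.3.2 and 2.1.3.3 list no separate time-to-eGFR-decrease endpoint, so that edit changes no planned result.

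The cost is one sentence and one derived date. The downside is that patients who die are taken as free of a renal event from the last sample to death, so a qualifying eGFR fall in that gap would be missed, while survivors still stop at the last sample. The reported renal incidence would be slightly lower than under the literal rule.

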**e. Censoring for severe hypoglycemia or AE (as part of general AE analysis)**

To keep the analysis of severe hypoglycemia consistent with the overall AE analysis, a patient without an adverse event will be considered censored at the date of last IMP taken + 10 days or

date of death, if earlier. For severe hypoglycemia, a patient without a severe hypoglycemia will be considered censored at the date of last IMP taken + 1 day or date of death, whichever earlier.

